Partial response (PR)	Any two of the parameters meet the following criteria at two consecutive, scheduled visit measurements at least 7 days apart during the study and no platelet transfusions within 7 days of platelet measurement (can still be a responder if ANC and reticulocyte measurements are valid): Absolute neutrophil count \geq 500/ μ L Platelet count \geq 20 000/ μ L Reticulocyte count \geq 60 000/ μ L (automated)
Patient Number (Patient No. NCDS)	A unique identifying number assigned to each patient who enrolls in the study
Period	A subdivision of the study timeline; divides stages into smaller functional segments such as screening, baseline, titration, washout, etc.
SAP	Statistical Analysis Plan (SAP), a regulatory document which provides evidence of preplanned statistical analyses
Stage related to study timeline	A major subdivision of the study timeline; begins and ends with major study milestones such as enrollment, randomization, completion of treatment, etc.

Study treatment	
Includes any drug or combination of drugs in any study arm administered to the patient (subject) as part of the required study procedures, including placebo and active drug run-ins.
 
In specific examples, it is important to judge investigational treatment component relationship relative to a study treatment combination; study treatment in this case refers to the investigational and non-investigational treatments in combination.

Study treatment discontinuation	Point/time when patient permanently stops taking study treatment for any reason
Supportive treatment	Refers to any treatment required by the exposure to a study treatment, e.g. premedication of vitamin supplementation and corticosteroid for pemetrexed disodium.
Variable	Identifier used in the data analysis; derived directly or indirectly from data collected using specified assessments at specified timepoints
Withdrawal of consent	Withdrawal of consent occurs only when a patient does not want to participate in the study any longer, and does not want any further visits or assessments, and does not want any further study related contact

Amendment 2: (15-Feb-2019)

Amendment rationale

As of 05-Oct-2018, 31 of the planned 50 patients were enrolled in the study.

Rationale for this amendment is based on findings in the study that identified the need to clarify patient selection and dose management.

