6.3 Dose modifications

6.3.1 Dose modification and dose delay

For patients who do not tolerate the protocol-specified dosing schedule, dose interruptions and/or reductions are mandated in order to allow patients to continue the study treatment.

These dose modifications are summarized in [Table 6-7](#). Deviations to mandatory dose interruptions and/or reductions are not allowed. Permanent treatment discontinuation is mandatory for specific events indicated as such in [Table 6-7](#) or listed in [Section 7.1.5.1](#).

These dose changes must be recorded on the Dosage Administration Record – electronic case report form (eCRF).

Common Terminology Criteria for Adverse Events Version 4.03 will be used for this study.

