> 3.0 - 5.0 x ULN	Maintain dose level. Repeat LFTs ^b as soon as possible, preferably within 48-72 hours from awareness of the abnormal results. If abnormal lab values are confirmed upon the repeat test, then monitor LFTs ^b weekly, or more frequently if clinically indicated, until resolved to $\leq 3.0 \times$ ULN Discontinue patient from the study treatment if elevation is combined with any of the following: 
• Clinical symptoms of liver injury or evidence for hepatic decompensation• Progressively increasing LFTs^b upon repeat testing• Persistence for ≥ 4 weeks
> 5.0 - 10.0 x ULN	Mandatory: Interrupt dose. Repeat LFTs ^b as soon as possible; preferably within 48-72 hours from awareness of the abnormal results. Monitor LFTs ^b weekly, or more frequently if clinically indicated until resolved to $\leq 3.0 \times$ ULN then:

Dose modifications for ETB115	
> 10.0 - 20.0 x ULN	If resolved in \leq 14 days, maintain dose level If resolved $>$ 14 days, decrease one dose level ^e Mandatory: Interrupt dose. Repeat LFTs ^b as soon as possible, preferably within 48-72 hours from awareness of the abnormal results. Monitor LFTs ^b weekly, or more frequently if clinically indicated until resolved to \leq baseline. Then decrease one dose level ^e .
> 20.0 x ULN	Mandatory: Discontinue patient from study drug treatment. Repeat LFTs ^b as soon as possible, preferably within 48-72 hours from awareness of the abnormal results. Monitor LFTs ^b weekly, or more frequently if clinically indicated until resolved to \leq baseline or stabilization over 4 weeks.
Combined^c elevations of AST or ALT and total bilirubin	
For patients with normal baseline ALT and AST and total bilirubin value, [AST or ALT $>$ 3.0 \times ULN] combined with [total bilirubin $>$ 2.0 \times ULN] without evidence of cholestasis ^d OR For patients with elevated baseline AST or ALT [AST or ALT $>$ 3 \times baseline] OR [AST or ALT $>$ 5.0 \times ULN], whichever is lower, combined with [total bilirubin $>$ 2 \times baseline AND $>$ 2.0 \times ULN]	Mandatory: Permanently discontinue patient from study drug treatment. Repeat as soon as possible, preferably within 48 hours from awareness of the abnormal results, then with weekly monitoring of LFTs ^b , or more frequently if clinically indicated, until AST, ALT, or bilirubin have resolved to baseline or stabilization over 4 weeks.

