
All dose modifications should be based on the worst preceding toxicity.
 
^a Common Toxicity Criteria for Adverse Events (CTCAE Version 4.03)
 
^b Core LFTs consist of ALT, AST, GGT, total bilirubin (fractionated [direct and indirect], if total bilirubin $>$ 2.0 \times ULN), and alkaline phosphatase (fractionated [quantification of isoforms], if alkaline phosphatase $>$ 2.0 \times ULN.)
 
^c "Combined" defined as total bilirubin increase to the defined threshold concurrently with ALT/AST increase to the defined threshold
 
If combined elevations of AST or ALT and total bilirubin do not meet the defined thresholds, please follow the instructions for isolated elevation of total bilirubin and isolated elevation of AST/ALT, and take a conservative action based on the degree of the elevations (e.g. discontinue treatment at the situation when omit dose is needed for one parameter and discontinue treatment is required for another parameter). After all elevations resolve to the defined thresholds that allow treatment re-initiation, re-start the treatment either at the same dose or at one dose lower if criterion for dose reduction is met.
 
^d "Cholestasis" defined as ALP elevation ($>$2.0 xULN and R value $<$2) in patients without bone metastasis, or elevation of ALP liver fraction in patients with bone metastasis. The R value is calculated by dividing the ALT by the ALP, using multiples of the ULN for both values. It denotes whether the relative pattern of ALT and/or ALP elevation is due to cholestatic (R \leq 2), hepatocellular (R \geq 5), or mixed (R $>$2 and $<$ 5) liver injury.
 
^e "One dose level" defined as eltrombopag dose reduction by 25 mg.
	

Eltrombopag can cause hepatobiliary laboratory abnormalities, severe hepatotoxicity, and potentially fatal liver injury. Serum ALT, AST and bilirubin should be measured prior to initiation of eltrombopag, every 2 weeks during the dose adjustment phase and monthly after establishment of a stable dose. Abnormal serum liver tests should be evaluated with repeat testing as described in [Table 6-7](#). If the abnormalities are confirmed, serum liver tests should be monitored weekly until the abnormalities resolve, stabilize, or return to baseline levels.

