6.3.4.1 Follow-up on potential drug-induced liver injury (DILI) cases

Patients with transaminase increase combined with TBIL increase may be indicative of potential DILI, and should be considered as clinically important events.

The threshold for potential DILI may depend on the patient's baseline AST/ALT and TBIL value; patients meeting any of the following criteria must require further follow-up as outlined below:

- For patients with normal ALT and AST and TBIL value at baseline: [AST or ALT > 3.0 x ULN] combined with [TBIL > 2.0 x ULN] OR [INR > 1.5] without evidence of cholestasis (no ALP elevation)
- For patients with elevated AST or ALT or TBIL value at baseline: [AST or ALT > 2 x baseline AND > 3.0 x ULN] OR [AST or ALT > 8.0 x ULN], combined with [TBIL > 2 x baseline AND > 2.0 x ULN]
- For subjects with normal baseline ALT: [ALT \geq 5.0 x ULN]

Medical review must ensure that liver test elevations are not caused by cholestasis, defined as ALP elevation > 2.0 x ULN with R value < 2 in patients without bone metastasis, or elevation of ALP liver fraction in patients with bone metastasis.

Note: (The R value is calculated by dividing the ALT by the ALP, using multiples of the ULN for both values. It denotes whether the relative pattern of ALT and/or ALP elevation is due to cholestatic (R \leq 2), hepatocellular (R \geq 5), or mixed (R > 2 and < 5) liver injury).

In the absence of cholestasis, these patients must be immediately discontinued from study drug treatment, and repeat LFT testing as soon as possible, preferably within 48 hours from the awareness of the abnormal results. The evaluation must include laboratory tests, detailed history, physical assessment and the possibility of liver metastasis or new liver lesions, obstructions/compressions, etc.

1. Laboratory tests must include ALT, AST, albumin, creatine kinase, total bilirubin, direct and indirect bilirubin, GGT, prothrombin time (PT)/INR and alkaline phosphatase.
2. A detailed history, including relevant information, such as review of ethanol, concomitant medications, herbal remedies, supplement consumption, history of any pre-existing liver conditions or risk factors, must be collected.
3. Further testing for acute hepatitis A, B, C or E infection and liver imaging (e.g., biliary tract) may be warranted.
4. Obtain PK sample, as close as possible to last dose of study drug, if PK analysis is performed in the study.

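### For normal-baseline ALT of 5.0 to 20×ULN without cholestasis, Section 6.3.4.1 stops study drug while Table 6-7 keeps or re-starts it, and no text says which prevails

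*Protocol*

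**What the plan says.** **Protocol 6.3.4.1.** Meeting any one of three criteria is enough. The third, which begins "For subjects with normal baseline ALT", is ALT ≥5.0×ULN with no bilirubin or INR condition. The order is: "In the absence of cholestasis, these patients must be immediately discontinued from study drug treatment". Repeat testing and a work-up follow. The section contains no re-start rule.

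**Protocol glossary.** Study treatment discontinuation is the "Point/time when patient permanently stops taking study treatment for any reason".

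**Protocol 6.3.1.1, Table 6-7, isolated AST or ALT rows.**
- >3–5×ULN: keep the dose. Discontinue if there is "Clinical symptoms of liver injury or evidence for hepatic decompensation", a progressive rise on repeat tests, or persistence for 4 weeks or more.
- >5–10×ULN: "Mandatory: Interrupt dose. Repeat LFTs". Treatment resumes once the value is ≤3×ULN. For recovery within two weeks the instruction ends "14 days, maintain dose level"; for slower recovery the dose falls by one level.
- >10–20×ULN: interrupt until back to baseline, then one level lower.
- >20×ULN: discontinue.

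**Table 6-7, note c.** When combined transaminase and bilirubin rises fall short of the combined thresholds, the site is to "take a conservative action based on the degree of the elevations".

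**Protocol 6.3.1.** "Permanent treatment discontinuation is mandatory for specific events indicated as such in" Table 6-7, or listed in Section 7.1.5.1.

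**The concern.** Both texts bind. Section 6.3.1.1 assigns isolated ALT/AST changes to Table 6-7, and Section 6.3.1 forbids departures from its mandatory steps. Section 6.3.4.1 is also written as an obligation. Two sites that each follow the protocol could treat the same patient differently, one ending eltrombopag and the other giving it again.

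This matters because Section 6.3.1.1 itself warns that eltrombopag can cause severe and possibly fatal liver injury. It also touches a reported outcome. Adverse events leading to discontinuation belong to secondary objective 9 (Protocol Table 3-1) and are summarised under SAP 2.7.1. That count would depend partly on which section a site read. The SAP foresees such values: SAP 2.7.3 tabulates ALT or AST above 5, 8, 10 and 20×ULN.

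**Working it through.** The plan states no figure here, so the check is a comparison of rules.

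**1. The two rules side by side** (normal baseline ALT, isolated rise, no cholestasis)

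| ALT (×ULN) | Table 6-7 | Section 6.3.4.1 | Agree? |
|---|---|---|---|
| 4.9 | keep dose, subject to that row's stop conditions | not triggered | yes |
| 5.0 | keep dose, same conditions | stop | no |
| 5.1, 8, 10 | hold; re-start at same dose (≤14 days) or 25 mg lower (>14 days) | stop | no |
| 15, 20 | hold; re-start 25 mg lower | stop | no |
| 20.1 | stop | stop | yes |

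The conflict covers 5.0 to 20×ULN inclusive. At 5.0 it is a single boundary value.

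**2. What it means for dose.** Starting doses are 150 mg, or 100 mg for Asian ancestry (6.1.1.1). One level is 25 mg (Table 6-7, note e). One level down is 150 − 25 = 125 mg, or 100 − 25 = 75 mg.
- Table 6-7 alone, >5–10×ULN: 150/100 mg again, or 125/75 mg.
- Table 6-7 alone, >10–20×ULN: 125/75 mg.
- Section 6.3.4.1: 0 mg throughout.

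Two further rules bear on these figures. Section 6.1.1.1 requires a lower daily dose after an interruption of more than 7 days or one caused by an adverse event, and Section 8.1.2.1 counts a laboratory abnormality that needs a protocol dose hold as an adverse event. On that reading even a prompt re-start would be at 125/75 mg. Section 6.3.1.1 also requires both drugs to be adjusted or interrupted when their liver effects cannot be separated, which could displace the keep-dose instruction at 5.0×ULN. The firm contrast is some re-exposure against none.

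**3. How far the cholestasis exemption reaches.** Without bone metastasis, cholestasis needs ALP >2×ULN and R = ALT/ALP <2, so ALP must exceed the larger of 2 and ALT/2.
- ALT 5: ALP >2.5×ULN.
- ALT 10: ALP >5×ULN.
- ALT 20: ALP >10×ULN.

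The exemption narrows as ALT rises and does not remove the conflict.

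**4. Search for a ranking rule**
- Note c covers only combined ALT/AST and bilirubin rises.
- Section 6.3.1 points to Section 7.1.5.1, which is the replacement policy.
- Section 6.3.4 sends the liver stop to Section 6.3.3.2, which holds only infection rules.
- Section 7.2.3 refers DILI cases to Section 6.3.1.1, but only for taking a PK sample.
- Section 2.6 names Sections 6.3.3 and 6.3.4 for hepatotoxicity guidance without ranking them against the table.

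**5. Frequency.** For the first-line triple-therapy study, Section 1.2.1.2.3 reports increased ALT in 29.3% with no split at 5×ULN. Four patients in the refractory study exceeded 5×ULN, but all four had raised ALT and/or AST at entry. Neither gives a rate for this group.

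**The case against.** **The stop may be only a pause.** Table 6-2 uses the word discontinue for a one-week hold, Section 6.3.1.2 speaks of temporary discontinuation, and Table 6-7 adds the word permanently only for combined rises. Section 6.3.4.1 goes straight on to repeat testing. A site could therefore stop, investigate, and then let Table 6-7 govern the re-start. This shows the wording is not uniform, but it is the weaker reading. The glossary makes discontinuation permanent, Table 6-7 separates interrupting from discontinuing, and Section 6.3.4.1 gives no route back to treatment.

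**Harmonising the other way is possible.** The documents report re-starts that went well: one refractory-study patient tolerated 150 mg again (1.2.1.2.2), and no hepatobiliary event in the first-line study led to discontinuation (1.2.1.2.3). This stands as a cost of the stricter choice. It does not remove the need to choose.

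**Timing.** SAP Section 1 puts the end of enrolment at 11-May-2020 and the primary-analysis lock at 09-Dec-2020, after all patients had completed or left the 6-month period. A change can no longer alter eltrombopag dosing in these patients. That stands too.

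**Stronger readings that the documents do not support.** A reader might infer that patients with liver symptoms above 5×ULN have no protection, because the symptom stop sits only in the >3–5×ULN row. The gap is narrow. It concerns isolated AST rises, raised-baseline ALT or a cholestatic pattern, with bilirubin and INR below their triggers. Those patients are held at once, Section 6.3.1.2 requires a stop for adverse events that make continuing difficult, and Section 7.1.5 lets the investigator stop. A reader might also infer that crossing 5×ULN cancels a stop already triggered by progressive rise. Section 6.3.1 makes the table's discontinuations mandatory, and nothing says a later row reverses one.

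**Conclusion.** The contradiction is real and should be corrected. For normal baseline ALT without cholestasis, the protocol gives two incompatible instructions from 5.0 to 20×ULN and does not rank them. Above 5×ULN the drug is held at once under both, so the issue is whether the patient is exposed again.

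This rests on reading discontinuation in Section 6.3.4.1 as permanent, and on the rise being isolated. Isolated AST rises and isolated rises from a raised baseline ALT do not meet the third criterion.

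A reader might infer a clean contrast of full dose against zero, or a number of affected patients. Section 6.1.1.1 undercuts the first, and the documents give no rate for the second. Nor does the point reach the sample size, the definition of response or the success rule.

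**What to change.** 1. Add a note to the isolated ALT/AST rows of Table 6-7: when a Section 6.3.4.1 criterion is met without cholestasis, Section 6.3.4.1 prevails and eltrombopag is not re-started.
2. Correct three references. In 6.3.1, keep Table 6-7 and replace 7.1.5.1 with Sections 6.3.1.2 and 6.3.4.1. In 6.3.4, replace 6.3.3.2 with Table 6-7 and Section 6.3.4.1. In 7.2.3, add 6.3.4.1 to the DILI reference. Pointing 6.3.1 or 6.3.4 to 6.3.4.1 alone would lose the non-liver stops in 6.3.1.2 or the bilirubin stops in Table 6-7.
3. As a minor safety addition, apply the existing stop for clinical liver injury or decompensation to every isolated ALT/AST row above 3×ULN.

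**Cost.** No extra tests or patients. A protocol amendment needs sponsor and ethics approval and, where required, health authority approval (Section 12.1). There may be a few more permanent eltrombopag stops, some in patients who would have tolerated a re-start.

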6.4 Concomitant medications

6.4.1 Permitted concomitant therapy

The patient must be told to notify the investigational site about any new medications he/she takes after the start of the study drug. All medications (other than study drug) and significant non-drug therapies (including physical therapy, herbal/natural medications and blood

transfusions) administered during the study must be listed on the Concomitant Medications or the Procedures and Significant Non-Drug Therapies eCRF.

6.4.1.1 Supportive Care

Transfusions for platelets and/or red blood cells should be limited in this study, however, must be given when medically needed.

Note that patients who have a platelet transfusion within 7 days of a scheduled visit platelet measurement and/or a pRBC transfusion within 14 days of a scheduled visit hemoglobin measurement will not be considered for PR or CR at that scheduled visit.

Platelet transfusions are recommended when:

- Platelet level is <10 000 / μ L, or
- Platelets <20 000/ μ L and with active bleeding or
- as medically necessary

RBC transfusions are recommended when:

- Hemoglobin is <8 g/dL, or if symptomatic according to local standard of care

Infection management

The use of antibiotics, anti-fungals, and granulocyte colony stimulating factor (G-CSF) is permitted. The local hospital guidelines for treatment of infections / febrile neutropenia should be followed.

6.4.2 Permitted concomitant therapy requiring caution and/or action

6.4.2.1 Eltrombopag

HMG-CoA Reductase Inhibitors (statins)

Patients will be permitted to use HMG-CoA reductase (3-hydroxy-3-methyl-glutaryl-CoA) inhibitors during the study, but these drugs should be used with caution and a 50% dose reduction of the HMG-CoA reductase inhibitor is recommended, with close monitoring for safety, such as liver chemistry and signs and symptoms of myolysis, and efficacy, such as cholesterol and triglycerides (refer to individual product information for monitoring recommendations).

Preclinical data showed that eltrombopag is an inhibitor of the transporters OATP1B1 and BCRP. Therefore, a clinical drug interaction study to evaluate the impact of eltrombopag on the PK of rosuvastatin, an OATP1B1 and BCRP substrate, was conducted in healthy patients. Co-administration of eltrombopag 75 mg once daily for 5 days with a single 10 mg dose of rosuvastatin administered on Day 5 increased plasma rosuvastatin Cmax 2.03-fold and AUCinf 55%.

Concomitant administration of eltrombopag and other OATP1B1 or BCRP substrates should be used with caution.

Polyvalent Cations (Chelation)

Eltrombopag chelates with polyvalent cations such as aluminum, calcium, iron, magnesium, selenium and zinc. Eltrombopag must be taken at least two hours before or four hours after any products such as antacids, dairy products, or mineral supplements containing polyvalent cations to avoid significant reduction in eltrombopag absorption.

Food Interaction

Administration of a single 50 mg-dose of eltrombopag with a standard high-calorie, high-fat breakfast that included dairy products reduced plasma eltrombopag AUC_{inf} by 59% (90% CI: 54%, 64%) and C_{max} by 65% (90% CI: 59%, 70%). Foods low in calcium (defined as <50 mg calcium per serving) including fruit, lean ham, beef and unfortified (no added calcium, magnesium, iron) fruit juice, unfortified soy milk, and unfortified grain did not significantly impact plasma eltrombopag exposure, regardless of calorie and fat content. To avoid significant reduction in eltrombopag absorption, eltrombopag must be taken at least two hours before or four hours after food containing >50 mg calcium and at least one hour before or two hours after food containing little (<50 mg) (or preferably no) calcium.

6.4.2.2 Cyclosporine

The concomitant use of cyclosporine with the following requires caution according to the local prescribing information:

- Potassium or potassium supplements, potassium-sparing diuretics, angiotensin converting enzyme inhibitors, angiotensin II receptor antagonists which may result in significant increases in serum potassium
- Medications which may decrease the concentration of cyclosporine; barbiturates, carbamazepine, oxcarbamazepine, phenytoin, nafcillin, sulfadimide, rifampicin, octreotide, probucol, orlistat, hypericum perforatum (St. John's wort), ticlopidine, sulfinpurazole, terbinafine, bosetan
- Medications which may increase the concentration of cyclosporine; macrolide antibiotics (erythromycin, azithromycin, clarithromycin), ketoconazole, fluconazole, itraconazole, voriconazole, diltiazem, nicardipine, verapamil, metoclopramide, oral contraceptives, danazol, methylprednisolone (high dose), allopurinol, amiodarone, cholic acid and derivatives, protease inhibitors, imatinib, colchicine, nefazadone
- Medications which may exhibit nephrotoxic synergy; aminoglycosides (gentamycin, tobramycin), amphotericin B, ciprofloxacin, vancomycin, trimethoprim (+ sulfamethoxazole), non-steroidal anti-inflammatory drugs (including diclofenac, naproxen, sulidac), melphalan, histamine H₂-receptor antagonists (cimetidine, ranitidine), methotrexate, tacrolimus
- Concomitant use with nifedipine may result in increased rate of gingival hyperplasia
- Cyclosporine is an inhibitor of CYP3A4 and P-glycoprotein and may increase plasma levels of co-medications that are substrates of this enzyme and/or transporter.
- Cyclosporine may reduce the clearance of digoxin, prednisolone, HMG-coA reductase inhibitors (statins), etoposide, aliskiren, bosetan or dabigatran. If co-administration is necessary, close clinical observation is required in order to enable early detection of

toxicity. Co-administration of cyclosporine increases blood/plasma concentrations of everolimus, sirolimus, repaglinide, bosetan, aliskiren, dabigatran, and the anthracyclines

